RSV infections result in high rates of hospitalization in infants, a large disease burden among infants and young children, and excess mortality in the elderly [Graham, 2011]. RSV infects 50-70% of infants during the first year of life and essentially all children will have had an RSV infection by their third birthday [Hall, 2004]. In the early months of life, infants may have protection against RSV through the maternal antibodies transferred to them during pregnancy. High titers of maternally derived RSV-neutralizing antibodies [Roca, 2002] have been shown to be inversely associated with the incidence of RSV associated-acute LRTI during the first 6 months of life, whereas incomplete transfer of maternally derived RSV-neutralizing antibodies has been implicated in the increased risk of severe RSV infection in preterm infants [de Sierra, 1993]. Previous infection with RSV does not prevent subsequent infections. Therefore, re-infection with RSV occurs throughout an individual's lifetime and is common in all age groups [Simoes, 1999; Krilov, 2011].

Globally, it is estimated that in children below 5 years of age, RSV causes >30 million acute lower respiratory infections (LRTI) each year resulting in more than 3 million hospitalizations, making it the most common cause of hospitalization for LRTI or all cause from any single pathogen in this age group [Nair, 2010]. RSV is the most common cause of bronchiolitis and pneumonia in children less than 1 year of age worldwide, with

highest risk in children less than 6 months of age [Nair, 2010; Langley, 2011]. A United States (US) based study conducted in children less than 18 years of age, found RSV in 58% of the hospitalizations for LRTI compared to parainfluenza virus 1-3 in 17%, influenza A/B in 21%, adenovirus in 2% and rhinovirus in 2% [Henrickson, 2004]. On a community level, a US day-care based study assessing the causes of respiratory tract infection (RTI) in children less than 1 year of age found that RSV infection was present in 11% of the cases, compared to rhinovirus in 35%, adenovirus in 22%, human coronavirus in 15%, parainfluenzavirus in 12%, human meta-pneumovirus in 4% and influenza A in 2% [Fairchok, 2010]. This difference between community and hospital proportions of RSV related infections indicates the propensity of RSV to cause more serious cases of RTI, mainly LRTI, compared to other viruses.

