9.7.1. Co-primary objectives

• To determine the total health burden of RSV-associated RTI with a suspicion of involvement of the lower respiratory tract.

Incidence rates will be calculated as the number of RSV-associated RTI with a suspicion of involvement of the lower respiratory tract over the number of children-years observations, overall and by subgroups.

Descriptive statistics of the different types of healthcare utilization from all healthcare settings will be provided (proportions, duration, etc.) among RSV-associated RTI with a suspicion of involvement of the lower respiratory tract, overall and by subgroups.

• To assess the performance of the LRTI case definition and severity scale for RSV-associated cases.

Incidences rates will be calculated as the number of RSV-associated LRTI/severe LRTI as classified by the LRTI case definition and severity scale and also as classified by the comparator case definitions (WHO and Nokes, et al [Modjarrad, 2016; Nokes, 2004]), over the number of children-years observations, overall and by subgroups.

Descriptive statistics of the different types of healthcare utilization will be provided (proportions, duration, etc.) among RSV-associated LRTI/severe LRTI as classified by the LRTI case definition and severity scale and also as classified by the comparator case definitions (WHO and Nokes, *et al* [Modjarrad, 2016; Nokes, 2004]), overall and by subgroups.

Statistical analysis of agreement will be performed to compare the different case definitions of RSV-associated LRTI/severe LRTI and key healthcare utilization and health outcomes (the hospitalization status, (P) intensive care unit [ICU] attendance, clinical diagnosis of bronchiolitis or pneumonia, death) overall and by age categories.

Table 15 Comparison of two classifications for severe/Non-severe LRTI

RSV-associated cases		Classification of reference (severe/Non-severe)		
		Hospitalized	Not hospitalized	
Alternative classification (severe / Non-severe)	Severe LRTI (LRTI case definition and severity scale)	True positive (TP)	False positive (FP)	
	Non-severe LRTI (LRTI case definition and severity scale)	False negative (FN)	True Negative (TN)	

2x2 contingency tables such as Table 15 will be provided and the following measures of agreement (with 95% CI) will be calculated:

- Sensitivity: TP/ (TP+FN)
- Specificity: TN/ (TN+FP)
- Positive predictive value (PPV): TP/ (TP+FP)
- Negative predictive value (NPV): TN/ (TN+FN)

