3. OBJECTIVES

3.1. Co-primary objectives

• To determine the total health burden* of RSV-associated RTI with a suspicion of involvement of the lower respiratory tract.

*Health burden refers to burden of the disease imposed on the study population in terms of incidence of the disease and associated healthcare utilization in any healthcare setting.

• To assess the performance of the LRTI case definition and severity scale for RSV associated cases.

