6.7. Health care utilization analysis

For this objective, the analysis will be based on PPS.

Descriptive statistics of the different types of healthcare utilization associated with disease severities will be produced by age interval and by country.

Please note that the heath care utilization reported here are only including medical care that subject were seeking outside the site clinics.

The number and percentage of all episodes(including recurrent) leading to outpatient visit, emergency room visit, Inpatient Admission-Non-Intensive Care, Inpatient Admission-ICU and No physician consultation outside site clinic will be displayed according for WHO RSV LRTI and WHO RSV severe LRTI cases.

The distribution (means and SD) of the number of days the usual care giver or another person took care of the child without missing work, the number of days a person had to stay home specifically because of the illness instead of going at work, and the number of days a person was hired to care for the child specifically because of the illness, will be displayed according to WHO RSV LRTI and WHO RSV severe LRTI status.

For clarity the type of health care utilization for RSV disease episodes is summarised in the table below showing endpoints and analytic methods.

200150 (EPI-RSV-005 BOD)

Statistical Analysis Plan Amendment 1 Final

Subgroup	Case definition	Endpoints	Event considered
By age categories and	WHO RSV LRTIWHO RSV severe	The number and proportion of episodes classified by	All events including
by country	LRTI	Outpatient visit	recurrent
		Emergency Room visit	oronto
		Inpatient Admission (non intensive care)	
		Inpatient Admission (intensive care)	
		No consultation other than site clinic	
		1 Other	
		• By episodes the mean and SD of:	
		The number of days the usual care giver or another person took care of the child without missing work	
		The number of days a person had to stay home specifically because of the illness instead of going at work	
		The number of days a person was hired to care for the child specifically because of the illness	

Table 13Summary of health care utilization for RSV disease episodes for
primary objectives

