- The risk factor analysis will be done using a Cox regression model and not a Poisson regression model to be consistent with the analysis performed in clinical trials.
- The sensitivity analysis will not be performed on the total enrolled cohort.
- The analysis of the impact of changes to the symptoms and threshold levels of symptoms in the LRTI case definition and severity scale will not be done by age category

200150 (EPI-RSV-005 BOD)

Statistical Analysis Plan Amendment 1 Final

- The date of study conclusion for subjects lost to follow-up will be the date of conclusion given in the CRF and will not be derived according to number of missed visits.
- Only first episode within a given age interval is considered for the computation of incidence. The incidence of event is computed using 3 different calculation methods: incidence rate, proportion affected, and incidence proportion. See section 11.1.1 for detail of calculation
- Sub-group of analysis for birth period outside or within transmission season will not be performed. Instead, the analysis will be based on the first 6 month of subject's life, and will be done considering 2 categories: <= 3 months and > 3 months. The incidence rate of RSV associate LRTI, severe LRTI, and hospitalization will be computed by country.
- Incidence and performance of case definition analysis (measures of agreement) will be performed using exploratory case definitions in anticipation of update to WHO case definitions.
- Analyses of cord blood collection using and not using recommended procedures will not be done. Instead, descriptive statistics for cord blood collection variables and cord blood levels of RSV A and B neutralizing antibodies according to cord blood collection variables will be provided. Additional analyses will be performed to evaluate disease surveillance and protocol procedures and include summary of number and percent of surveillance contacts followed by an exam visit, the duration between surveillance contact and exam visit, and duration between nasal swap and onset of symptoms.

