11. ANNEX 1 STANDARD DATA DERIVATION RULE AND STATISTICAL METHODS

11.1. Statistical Method References

11.1.1. Computation of incidence rates

For each endpoint, the incidence rate (IR, number of episodes/endpoints per 100 personyears) will be calculated by dividing the number of subjects reporting first episode over the follow-up period by the total person-year. A 95% CI will be computed using an exact method for a Poisson variable as described below.

The person-time at risk for an event of interest (e.g. RSV-LRTI) will be calculated as the time between the date of birth and the end of the at-risk period or the earliest of the followings:

200150 (EPI-RSV-005 BOD)

Statistical Analysis Plan Amendment 1 Final

- Date of first diagnosis of event of interest (e.g. first episode of RSV-LRTI);
- Date when child reaches 2 years;
- Date of last contact (lost-to follow-up, defined as no contact by the subject's parent(s)/LAR(s) over the period of 3 planned contacts and/or 2 months and after a final attempt has been made by mail. Once this has been reached, the subject is censored at the time of last contact);
- Date of death.

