
Center	Total N =	
	n	%

N = number of subjects of total enrolled cohort

n = number of subjects enrolled for a given center

Center = GSK biologicals assigned center number

% = n/N

- 12.3. Incidence
- 12.3.1. Primary incidence analysis
- 12.3.1.1. (PO1) To determine the total health burden* of RSV-associated RTI with a suspicion of involvement of the lower respiratory tract
- Template 7 Incidence rate of first episode of [RSV RTI with suspicion of involvement of LRT, WHO RSV LRTI, WHO RSV severe LRTI, RSV hospitalization, WHO RSV LRTI hospitalization, WHO RSV severe LRTI hospitalization], by age interval overall and by country (PPS)

						95% exact Cl	
Country	Age interval (Months)	Total number of subjects	Total number of first episode	Total number of person- years	Incidence rate (100 person- years)	LL	UL
Overall	0-5						
	6-11						
	0-11						
	12-23						
	0-23						
<each country=""></each>							1

Incidence rate computed using the number of first episode as numerator and the total number of person-years over the entire follow-up as denominator

CI=confidence interval, LL, UL for incidence = Exact 95% Lower and Upper confidence limits

Template 8 Incidence rate of first episode of WHO RSV LRTI, WHO RSV severe LRTI, RSV hospitalization, by age interval – by country (PPS)

		95% exact CI						
Country	Age interval	Episodes	Total number of subjects	Total number of first episode	Total number of person- years	Incidence rate (100 person- years)	LL	UL
<each country ></each 	0-11 months	WHO RSV LRTI						
		WHO RSV severe LRTI						
		RSV hospitalization						
	12-23 months	WHO RSV LRTI						
		WHO RSV severe LRTI						
		RSV hospitalization						

Incidence rate computed using the number of first episode as numerator and the total number of person-years over the entire follow-up as denominator

CI=confidence interval, LL, UL for incidence = Exact 95% Lower and Upper confidence limits
Statistical Analysis Plan Amendment 1 Final

Template 9 Proportion affected by at least one episode of [RSV RTI with suspicion of involvement of LRT, WHO RSV LRTI, WHO RSV severe LRTI, RSV hospitalization, WHO RSV LRTI hospitalization, WHO RSV severe LRTI hospitalization] by age interval – overall and by country (PPS)

					95% e	xact Cl
Country	Age interval (Months)	Total number of subjects at birth	Total number of subjects affected	Proportion affected	LL	UL
Overall	0-5					
	6-11					
	0-11					
	12-23					
	0-23					
<each country=""></each>						

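### Incidence is restricted to each child's first episode per age interval, so the co-primary burden objective has no all-episode rate, and the denominator of the first-episode rate is stated in conflicting ways

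*SAP*

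**What the plan says.** The co-primary objective is unchanged between protocol and SAP: "To determine the total health burden* of RSV-associated RTI with a suspicion of involvement of the lower respiratory tract". The protocol defines health burden as incidence plus associated healthcare use. For incidence, protocol 9.7.1 reads "Incidence rates will be calculated as the number of RSV-associated RTI with a suspicion of involvement of the lower respiratory tract over" child-years, with no limit to first episodes. Protocol section 4.1 treats an LRTI after at least 7 symptom-free days as a new case, and protocol 1.1.1 notes that "Previous infection with RSV does not prevent subsequent infections".

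SAP section 9 then lists a change: "Only first episode within a given age interval is considered for the computation of incidence". SAP 11.1.1 obtains the rate by "dividing the number of subjects reporting first episode over the follow-up period by the total person-year", and ends person-time at the earliest of several dates, one being "Date of first diagnosis of event of interest (e.g. first episode of RSV-LRTI". The Template 7 footnote instead describes the "total number of person-years over the entire follow-up as denominator", and the Template 15 footnote refers to person-years over the age interval.

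Healthcare use is tabulated differently. SAP 6.7 reports "The number and percentage of all episodes(including recurrent) leading to outpatient visit" and other types of care, for WHO RSV LRTI and severe LRTI. The agreement analyses in SAP 6.8.1 also use all episodes.

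**The concern.** A burden objective asks how many illnesses occur per child-year. A first-episode rate estimates how quickly children have their first one. The SAP replaces the protocol's quantity with the second and gives no reason, although the same list does explain the move from Poisson to Cox regression.

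No other output restores the repeats. Incidence proportion and Kaplan-Meier concern first episodes. SAP Table 12 labels one measure as the proportion affected by all new episodes, but SAP 11.1.3 defines it as children with at least one episode, so the label is wrong.

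The two halves of the burden objective therefore rest on different episode sets. For WHO RSV LRTI and severe LRTI, the healthcare tables give all-episode counts with no matching rate, child-years or confidence interval. For the event named in the objective, RSV RTI with suspected lower-tract involvement, neither an all-episode rate nor a healthcare table is planned.

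**Working it through.** **Plan's own figure.** The documents give no repeat-episode rate. The input used here is the hospitalization rate in protocol 9.3, whose worked example reproduces. For 6 cases in 320 child-years, χ²(0.025; 12)/2/320 = 6.9 and χ²(0.975; 14)/2/320 = 40.8 per 1000. With design effect 1 + 159 × 0.02 = 4.18, the upper normal limit is 20 + 1.96 × √(4.18 × 0.020/320) × 1000 = 51.7 per 1000.

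**Inputs.**
- Hospitalization: 10–50 per 1000 child-years in the first year of life (protocol 9.3).
- RSV LRTI: 8 times that (protocol 9.3), so L = 0.08–0.40 per child-year in year 1.
- Second-year decline: three sources in protocol Table 12 report 12–23 months. The ratio r of year 2 to the year-1 average is 2.7/((16.9 + 5.1)/2) = 0.245, 3.7/((44.1 + 15.0)/2) = 0.125 and 0.4/((18.5 + 7.4)/2) = 0.031. These are hospitalization ratios; applying them to LRTI is an assumption.
- Differences in proneness between children: gamma frailty, variance v = 0.5–1.0 (assumption).

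**Share of episodes that are not first, 24 months, no frailty.** Expected episodes per child H = L(1 + r); children with a first episode = 1 − exp(−H); share = 1 − (1 − exp(−H))/H. For L = 0.40 and r = 0.245, H = 0.498, first = 0.392, share = 21.2%.

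| L | flat (r = 1) | r = 0.245 | r = 0.125 | r = 0.031 |
|---|---|---|---|---|
| 0.08 | 7.6% | 4.8% | 4.4% | 4.0% |
| 0.16 | 14.4% | 9.3% | 8.5% | 7.8% |
| 0.40 | 31.2% | 21.2% | 19.5% | 18.1% |

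Hospitalization at a flat 10–50 per 1000: 1 − (1 − exp(−0.02))/0.02 = 1.0%, to 1 − (1 − exp(−0.10))/0.10 = 4.8%.

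Frailty raises the share. With v = 1, first = H/(1 + H); at L = 0.40 and r = 0.245 this is 0.498/1.498 = 0.333, so the share is 33%.

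**Bias in the rate, person-time stopped at the first event.**
- Constant hazard, no frailty: the first-episode rate equals the all-episode rate (0.160 against 0.160 at L = 0.16).
- Hazard falling with age, no frailty: person-time per child = (1 − exp(−L))/L + exp(−L)(1 − exp(−rL))/(rL). At L = 0.40 and r = 0.031 this is 1.490, so the rate is 0.338/1.490 = 0.227 against 0.412/2 = 0.206, 10% too high. Other combinations are 1.5–9% too high.
- Falling hazard with frailty v = 1: person-time = ln(1 + L)/L + ln((1 + L + rL)/(1 + L))/(rL). At L = 0.40 and r = 0.245 this is 0.841 + 0.690 = 1.531, so the rate is 0.3325/1.531 = 0.217 against 0.498/2 = 0.249, 13% too low. This is the largest shortfall for v = 0.5–1.0 with the decline.
- Flat hazard with v = 1 at L = 0.40: 0.3025 against 0.400, 24% too low.

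**Bias if person-time is not stopped.** The denominator is the same as for the all-episode rate, so the shortfall equals the omitted share. At a flat 0.16: 0.274/2 = 0.137 against 0.160, 14.4% too low.

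**The case against.** The departure is openly listed in SAP section 9, and protocol 9.10 commits the final report to justifying changes. A first-episode rate is a legitimate quantity, and with person-time stopped at the event it need not be biased. The first-episode rule works within intervals, and SAP section 9 prefers pooled incidence by year of life. On that scale the non-first share without frailty is 4–18% in year 1 (1 − (1 − exp(−L))/L at L = 0.08 and 0.40) and under 5% in year 2. The protocol says reinfection occurs but gives no rate of repeat RSV LRTI before age 2.

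All of this stands, and it limits the size. It does not supply a reason for the change or an all-episode rate.

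Three stronger readings are tempting, and the documents do not support them:
- **That incidence is understated by the omitted share.** This holds only if person-time runs on after the first event. Under SAP 11.1.1 the direction is uncertain.
- **That healthcare use per child-year cannot be formed.** Template 18 gives all-episode counts by type of care, age and country for WHO RSV LRTI and severe LRTI. What is missing is an unstopped child-years denominator and an interval.
- **That most all-cause episodes are lost.** The same rule applies to that secondary analysis (SAP 6.6.2), but the documents give no all-cause episode rate from which to size it.

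**Conclusion.** The concern holds as an unexplained departure that leaves the protocol's burden rate unreported. Under the protocol's expected rates, about 4–21% of RSV LRTI episodes over 24 months would fall outside the incidence count. This assumes that the Table 12 decline applies to LRTI, that there is no frailty and that children have complete follow-up. The share is 8–31% if the rate stays flat, and about 1–5% for hospitalization at a flat rate.

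With person-time stopped, the first-episode rate is unbiased under a constant homogeneous hazard, up to about 10% too high if the hazard falls with age, and up to about 13% too low with frailty plus that fall (24% with frailty and a flat rate). These are illustrations, since the frailty variance is assumed. A reader of the planned tables could not tell which case applies.

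The denominator conflict between SAP 11.1.1 and the footnotes to Templates 7 and 15 is a separate and definite problem, because it decides whether the reported rate carries the full shortfall. The point merits a change to the SAP but does not undermine the study's data.

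**What to change.** - For each endpoint in SAP Table 12 and Template 15, add an all-episode rate: new episodes by the rule in SAP 11.2.1.12, divided by all child-years observed in the interval and not stopped at the first episode. Use a robust confidence interval clustered on the child, since an exact Poisson interval ignores repeat episodes within a child.
- Name this rate as the burden estimate, keep the first-episode rates beside it, and state why they were introduced.
- Correct the Table 12 label so that it describes children with at least one episode.
- Make the person-time wording in SAP 11.1.1 and in the footnotes to Templates 7 and 15 agree.

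The cost is one more column per incidence table. The new-episode rule is already written, and episode-level data already feed SAP 6.7 and 6.8.1, so no new data are needed.

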10. LIST OF FINAL REPORT TABLES, LISTINGS AND FIGURES

The list of final report tables, listing and figures are available in the TOC document.

11. ANNEX 1 STANDARD DATA DERIVATION RULE AND STATISTICAL METHODS

11.1. Statistical Method References

11.1.1. Computation of incidence rates

For each endpoint, the incidence rate (IR, number of episodes/endpoints per 100 personyears) will be calculated by dividing the number of subjects reporting first episode over the follow-up period by the total person-year. A 95% CI will be computed using an exact method for a Poisson variable as described below.

The person-time at risk for an event of interest (e.g. RSV-LRTI) will be calculated as the time between the date of birth and the end of the at-risk period or the earliest of the followings:

200150 (EPI-RSV-005 BOD)

Statistical Analysis Plan Amendment 1 Final

- Date of first diagnosis of event of interest (e.g. first episode of RSV-LRTI);
- Date when child reaches 2 years;
- Date of last contact (lost-to follow-up, defined as no contact by the subject's parent(s)/LAR(s) over the period of 3 planned contacts and/or 2 months and after a final attempt has been made by mail. Once this has been reached, the subject is censored at the time of last contact);
- Date of death.

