	1280	64	50	[38.5; 63.8]	[25.0; 75.0]			
Second year of enrollment (analysis will be performed 1 year after the last subject is recruited)								
Country/region level	160	2	10	[0.7; 40.1]	[0; 41.7]			
	160	3	20	[3.9; 54.8]	[0; 64.8]			
	160	5	30	[8.4; 68.5]	[0; 84.9]			
	160	6	40	[13.8; 81.6]	[0; 103.4]			
	160	8	50	[21.6; 98.5]	[0; 120.8]			
Overall	640	6	10	[3.4; 20.4]	[0; 25.8]			
	640	13	20	[10.2; 33.7]	[0; 42.4]			
	640	19	30	[17.9; 46.4]	[2.6; 57.4]			
	640	26	40	[25.9; 58.6]	[8.3; 71.7]			
	640	32	50	[34.2; 70.6]	[14.6; 85.4]			

CI = Confidence Interval; RSV = Respiratory Syncytial Virus; LRTI = Lower Respiratory Tract Infection; DE = Design Effect

The design effect measures the increase in the standard error of the estimate due to the sampling design. The following formula will be used to estimate the design effect in the simulation [Bennett, 1991]:

$$DE = \frac{s^2_{cluster \ sample}}{s^2_{simple \ random \ sample}}$$

With

$$s_{cluster \, SAMPLE}^{2} = (c/\sum_{i} x_{i})^{2} (\sum_{i} y_{i}^{2} - 2p \sum_{i} x_{i} y_{i} + p^{2} \sum_{i} x_{i}^{2}) / [c(c-1)]$$

$$s^2_{SIMPLE RANDOM SAMPLE} = p(1-p)/n$$
Where, 'c' is the number of clusters, 'x_i', and 'y_i' are number of children-years and number of cases, respectively in the 'ith' cluster, 'n' is the total number of children-years and 'p' is the overall proportion ' $\sum y_i/\sum x_i$ '.

The intra-cluster correlation ' ρ ' may then be estimated as:

$$\rho = (DE - 1)/[(\sum x_i/c) - 1]$$

Each simulation consists of creating 'c' clusters whose size and incidence vary around a given value. Then the above formula was applied to estimate the design effect in the simulation. Table 14 shows the median result of 1000 simulations (with 5th and 95th percentile). The design effect [Bennett, 1991] can be estimated as following once the intra-cluster correlation value is known or can be assumed:

$$DE = 1 + (b - 1) \rho$$

Where, ρ is the intra-cluster correlation and b is the average number of subjects sampled per cluster. According to the results of simulations, we could assume that the intra-cluster correlation of 0.02 (See Table 14 below) and considering 12 clusters of 160 subjects, we expect that the design effect will take a value of 4.18.

Table 14	Design effect calculated from 1000 simulations and for different
	hypothesis

Hypothesis of the	Results of 1000 simulations				

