simulation (Number of clusters; Overall number of children- years; incidence)	Number of children-years by cluster (P5; Median; P95)	Proportion of cases by cluster (P5; Median; P95)	DE : Design Effect (P5; Median; P95)	ρ : intra-cluster correlation (P5; Median; P95)	
9; 2400; 0.03	136; 266; 401	0; 0.028; 0.086	2.51; 6.46; 13.67	0.006; 0.021; 0.047	
12; 2400; 0.03	100; 201; 300	0; 0.027; 0.087	2.57; 5.13; 9.49	0.008; 0.021; 0.042	
15; 2400; 0.03	81; 160; 239	0; 0.027; 0.088	2.29; 4.34; 7.74	0.008; 0.021; 0.042	
18; 2400; 0.03	68; 133; 199	0; 0.026; 0.091	2.08; 3.89; 6.69	0.009; 0.022; 0.043	

P = Percentile

Few active studies reported the overall RSV-associated LRTI incidence rates (with or without hospitalization). According to the results observed in a birth cohort conducted in Kenya [Nokes, 2008] we expect that the RSV-associated LRTI rate will be 8 times greater than the hospitalization rate.

As the subjects may dropout from the study due to a variety of reasons, e.g. migration from the study area, the sample size has been increased to accommodate the same. Assuming a drop-out rate of about 20% during the course of follow-up approximately 400 subjects by country/region and 2400 subjects overall will need to be recruited.

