9.5.1. General considerations for statistical analyses

The primary analyses will at least be performed on the **PPS** cohort or sub-cohort. If more than 5% of the subjects are eliminated from the total enrolled cohort, then all analyses **may** also be performed on the total enrolled cohort in addition to the **PPS** cohort or sub-cohort.

When mentioned below in the upcoming analyses sections, analysis by subgroups *may* include:

- Age categories
- Hemisphere/Region/Country
- Birth on-season or off-season
- Collection time of swabs (72 hours/48 hours from the start date of the case (date of the call), 72 hours/48 hours from the reported onset of symptoms).

• For all incidence rate calculations, the 95% CI using the exact Poisson distribution will be estimated, as well the 95% CI using the normal approximation of the Poisson distribution, accounting for a design effect (after having derived the design effect from the real data).

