9.10. Conduct of analyses

Analytic plans may be modified as appropriate to accommodate final sample sizes and data distributions. Any deviation(s) or change(s) from the original statistical plan outlined in this protocol will be described and justified in the final study report.

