6.6. Incidence analysis

6.6.1. Analysis of co-primary objectives: incidence of RSV respiratory disease

For this objective, the analysis will be based on PPS.

For clarity the analysis of RSV disease incidence is summarised in the table below showing endpoints and analytic methods.

200150 (EPI-RSV-005 BOD)

Statistical Analysis Plan Amendment 1 Final

For each of the following endpoints you could find the case definitions in Table 4:

- RSV RTI with suspicion of involvement of LRT
- WHO RSV LRTI
- WHO RSV LRTI hospitalisation
- WHO RSV severe LRTI
- WHO RSV severe LRTI hospitalisation
- WHO RSV hospitalisation

Table 12Summary of RSV incidence analyses for primary objectives

Endpoints	Incidence analysis method	Subgroup
RSV RTI with suspicion of involvement of LRT WHO RSV LRTI WHO RSV severe LRTI RSV hospitalisation WHO RSV LRTI hospitalisation WHO RSV severe LRTI hospitalisation	Incidence rates of first episode Cumulative probability of first episode (Kaplan Meier)	Overall, by country, by age intervals, by transmission interval
RSV RTI with suspicion of involvement of LRT WHO RSV LRTI WHO RSV severe LRTI RSV hospitalisation WHO RSV LRTI hospitalisation WHO RSV severe LRTI hospitalisation	Proportion affected by all new episodes	Overall and by country, by age intervals
RSV RTI with suspicion of involvement of LRT WHO RSV LRTI WHO RSV severe LRTI RSV hospitalisation WHO RSV LRTI hospitalisation WHO RSV severe LRTI hospitalisation	Incidence proportion of first episode	Overall and by country, by monthly age

For each endpoints listed in the previous table the 95% CI will be computed as described in section 11.1.2 depending on the age category considered and the method listed in the analysis column. Kaplan-Meier curves presenting the cumulative probability of first episode will be displayed overall and by country. The cumulative probability of presenting first episode will be given with its 95% CI at the end of the follow-up.

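### The SAP drops the protocol's design-effect interval for incidence rates without listing the change, leaving the pooled eight-country rates with an exact Poisson interval only

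*SAP*

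**What the plan says.** Protocol 9.5.1 applies to all incidence rate calculations. It asks for the exact Poisson interval, "as well the 95% CI using the normal approximation of the Poisson distribution, accounting for a design effect", with the design effect derived from the real data. Protocol 9.3 plans on that basis: "we expect that the design effect will take a value of 4.18", and Table 13 prints both intervals in every row, country and overall.

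SAP 6.6.1 sends the co-primary incidence intervals to one place: "For each endpoints listed in the previous table the 95% CI will be computed as described in section 11.1.2". SAP 11.1.1 says "A 95% CI will be computed using an exact method for a Poisson variable as described below", and 11.1.2 gives the chi-squared form of the exact limits with no design-effect term. The incidence-rate templates (7, 8, 12, 15 and 34) have columns for exact limits only. In the SAP the design effect survives only in the list of abbreviations.

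SAP section 9 records several changes to the incidence analysis: first episodes only, three calculation methods, and pooling across countries limited to year of life. It does not record the loss of the second interval. On changes, protocol 9.10 says: "Any deviation(s) or change(s) from the original statistical plan outlined in this protocol will be described and justified in the final study report".

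**The concern.** Both documents describe the analyses as descriptive, so the interval is the main statement of precision. Template 7 serves a co-primary objective, and its Overall rows pool eight countries; Template 15 (secondary) and Template 34 (exploratory definitions) do the same. SAP section 9 itself calls the settings diverse. An interval that assumes no clustering is hardest to defend on exactly these rows, and the protocol had foreseen the problem. Because section 9 is silent, nothing in the SAP would prompt the authors of the study report to explain why the second interval is missing.

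**Working it through.** **Inputs.** From protocol 9.3: correlation 0.02; 12 clusters of 160 subjects; the Table 13 intervals; the Table 14 results for 12 clusters, with correlation 0.008 (5th percentile) and 0.042 (95th percentile) and design effect "2.57; 5.13; 9.49" (5th percentile, median, 95th percentile). From protocol 5.1: about 1920 evaluable subjects. Assumed here: about 1920 child-years in the pooled 0-11 month row (one year per evaluable child, before censoring at first episode) and equal clusters.

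**Reproducing the plan's figures.** DE = 1 + (b - 1) × rho = 1 + 159 × 0.02 = 4.18. The adjusted interval is rate ± 1.96 × sqrt(DE × rate / T), with T in child-years and the lower limit cut at 0. At 20 per 1000 and T = 1280 this gives [4.2; 35.8], as printed in Table 13, against a printed exact interval of [13.0; 29.3]. The widths are 31.6 and 16.3.

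**Which T applies to the SAP.** The 1280 and 640 child-years in Table 13 are enrolment-year strata. The SAP reports by age interval over the whole cohort, so neither figure is a row of Template 7.

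**Unit of cluster size.** The protocol defines it in subjects for the planning formula ("b is the average number of subjects sampled per cluster"), but in the variance formula the x and y terms "are number of children-years and number of cases, respectively in the" i-th cluster. Table 14 follows the second convention: (5.13 - 1)/(200 - 1) = 0.021, with 200 = 2400/12 child-years per cluster. For a 0-11 month row of 1920 child-years the choice makes no difference: 1920/12 = 160 on either count, so DE = 4.18.

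**Pooled 0-11 month row at 20 per 1000.** The expected count is 0.020 × 1920 = 38.4, taken as 38. The exact limits by the SAP 11.1.2 formula are [14.0; 27.2], width 13.2. Adjusted limits by correlation:

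| Correlation | DE = 1 + 159 × rho | Adjusted interval per 1000 | Exact width / adjusted width |
|---|---|---|---|
| 0.008 | 2.27 | [10.5; 29.5] | 0.69 |
| 0.02 | 4.18 | [7.1; 32.9] | 0.51 |
| 0.042 | 7.68 | [2.5; 37.5] | 0.38 |

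**Separate minor point.** SAP 11.1.3 gives the proportion affected, a binomial quantity, a Poisson interval, although SAP 6.9.2 already uses Clopper-Pearson. With an assumed n = 1920, Poisson against Clopper-Pearson limits in percent are: 38 events (2%), [1.40; 2.72] against [1.40; 2.71], about 1% wider; 96 events (5%), [4.05; 6.11] against [4.07; 6.07], about 3% wider; 384 events (20%), [18.05; 22.10] against [18.23; 21.86], about 12% wider. The error is conservative.

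**The case against.** The strongest reply is that the exact interval is not wrong in itself. If centres simply have different fixed rates, the pooled count is a sum of independent Poisson counts and the exact interval is valid for this cohort. It becomes too narrow only if the centres are treated as a sample from a wider population, or if cases within a centre depend on one another, as in an outbreak. The documents do not describe random selection of centres. This stands, and it makes the conclusion conditional.

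The country rows printed below each Overall row let the reader see heterogeneity, and SAP section 9 plays down pooled results. That is true, but the pooled rows remain in the templates, and country rows do not supply an interval for a pooled rate.

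The interval to be restored is also imperfect. Its lower limit is 0 in 13 of the 20 rows of Table 13, including every country row, and design effects estimated from few events will be unstable. This argues for printing the estimate and the number of clusters, and for an explicit exception for small country rows. It does not justify dropping the interval unannounced.

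A reader might infer that the SAP already breaches protocol 9.10. It does not: that section allows analytic plans to be modified and places the justification in the final study report. A reader might also take the 1280 and 640 child-year rows of Table 13, count cluster size in child-years, and conclude that the loss is smaller than the planning value implies. The documents do not support that for the pooled 0-11 month row, because those figures are not SAP rows.

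**Conclusion.** The departure is certain: the protocol requires two intervals for all incidence rates, the SAP keeps one, and section 9 does not say so. It is an unlisted departure from protocol 9.5.1 that can still be put right. The country rows, including those in Templates 8 and 12, lose the interval too, but the main consequence is for the pooled rows of Templates 7, 15 and 34.

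The size is not known. If clustering matters in either sense above, the exact interval on a pooled 0-11 month row would be about half the adjusted width at the planning correlation, and from about 0.7 down to 0.4 of it over the range in Table 14. This rests on 1920 child-years, 12 equal clusters, a rate of 20 per 1000, and a correlation that comes from the protocol's simulations. A reader might conclude that the pooled intervals will be half as wide as they should be; the documents do not support that as a finding, because the protocol leaves the real design effect to be estimated from the data. The change should be made, because the protocol's own safeguard can be restored from data already held.

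**What to change.** In SAP 11.1.2, restore the protocol's design-effect interval beside the exact one, at least for the pooled 0-11 and 12-23 month rows of Templates 7, 15 and 34, which are the pooled rows that section 9 says it keeps. Use the protocol 9.3 variance formula. State the cluster unit in advance (for example study centre, noting that between-country differences then enter the design effect), and print the estimated design effect and the number of clusters. Wherever the interval is not given, for example in country rows with few centres, list and justify the omission in SAP section 9. Separately, in SAP 11.1.3 use an exact binomial (Clopper-Pearson) interval for the proportion affected.

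The cost is extra columns in three templates and (6 + 3 + 2) endpoints × 2 age intervals = 22 design-effect estimates, or 11 × 5 = 55 if all five pooled age rows stay. If country rows qualify, Templates 8 and 12 need the columns too. Estimates for rare endpoints will be unstable, and the stated precision of the pooled rates will look less favourable. No new data are needed.
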